#### **8.6.2 Assessment of target (plaque) background (blood) ratio with PET/CT**

Patients will have two PET/CT scans with labelled glucose  $^{18}\text{F}$ -deoxyglucose at Baseline and Week 24 only at the sites appropriately equipped.

The baseline PET/CT scan can be done anytime during the screening period, before the randomization.

All images will be collected for their review by an expert, with a window of +/- 7 days around the strict date.

The detailed procedure for performing and collecting PET/CT scans will be outlined in the Imaging Manual.

#### **8.7 Assessments and Procedures for Patients who Prematurely Discontinue Study Medication during double-blind treatment period**

Patients who withdraw from study medication should come to the site for a safety follow-up, 4 weeks after the last dose: the same safety assessments as the ones planned for study completer's week 52 visit (V31) should be performed.

Additionally:

- In case the study medication is stopped prematurely prior to week 24 (V18), a 3T-MRI should be performed as soon as possible after study drug discontinuation. If the patient agrees to stay in the study, he/she will be asked to come back at the site for full assessments as per protocol every 8 weeks until visit V30 and a last 3T-MRI will be performed at visit V30.
- In case the study drug is stopped during the extension treatment period (i.e. after week 24 (visit V18), patient should come back to the site for full assessments as per protocol every 8 weeks until week 48, a last 3T-MRI will be done at week 48.

All AEs (related or not related) must be reported until the final study evaluation at visit V30 and thereafter only the SAEs likely to be related to the study drug or study procedures must be notified.

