### **8.3 Clinical Assessments and Procedures during the Double-blind Treatment Period**

Patients will visit the clinic each week for the first 8 weeks and every 2 weeks thereafter until the end of the treatment period (week 48) as described in Appendix A. At each visit, the patient will receive an infusion and will be checked for:

- Adverse events
- Previous and concomitant medications

Complete assessments as described for visit 2 (see *Section 8.2* above) will be performed 4 weeks and 8 weeks after randomization (at visit 6 and visit 10). Thereafter, patients will have complete assessments every 8 weeks until the end of the week 48 treatment period (at week 16, 24, 32, 40 and 48). Unless otherwise specified, blood and urine specimens will be collected prior to study drug dosing.

Markers of inflammation, oxidation, lipid metabolism and CV risk (See *Section 8.10*) will be assessed at baseline, week 8, week 24 and week 48 (end of treatment).

HbA1c assessment will be performed only at baseline (See *Appendix A*).

Anti-ApoA-1 antibody assessment will be performed at week 8, week 24 and week 48 (end of treatment).

Blood samples will be collected for biomarkers assessments at week 24.

A blood sample will also be drawn two hours after initiation of the infusion to assess the PK, at week 24.

Follow-up 3T-MRI will be done at the end of the induction treatment phase (week 8), week 24 and at the end of the overall week 48 treatment period.

Follow-up FDG-PET/CT will be performed only once 24 weeks after randomization.

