## 8.5 Safety Follow-up

### For patients treated until week 48:

Patients will be instructed to fast prior to the visit. A safety follow-up for all patients will be conducted 4 weeks (+/- 7 days) after the final dose of study medication and will include,

- Physical exam (See Section 8.8.1)
- Blood Pressure and Heart Rate
- Vital signs (See Section 8.8.2)
- ECG (See Section 8.8.3)
- Previous and concomitant treatments
- Adverse Events
- Urinalysis (See Section 8.8.4)
- Blood samples for
  - Serum biochemistry (See Section 8.8.4)
  - Hematology and coagulation (See Section 8.8.4)

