### **8.8.5 Immunogenicity Testing**

Specimen will be collected for anti-ApoA-1 antibody testing at the screening visit, week 8, 24 and end of treatment period. If patients have a positive result for the presence of neutralizing anti-ApoA1 antibody at the end of treatment period visit, the patients must return monthly for testing until the antibodies return to screening value. Collection tubes will be supplied by the central laboratory as part of the visit specific kits for these visits. Collection, processing and shipment instructions will be located in the Laboratory Manual provided to the study sites. The clinical sites will send batch shipments of samples to the central laboratory monthly or sooner depending on local site requirements. An aliquot for specimens that test positive for Anti-ApoA-1 antibody testing will be analyzed for neutralizing antibody activity.

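### No anti-ApoA-1 antibody sample is required when a patient stops study drug early, so a patient who stops before week 8 and then leaves has no post-dose result

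*Protocol*

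**What the plan says.** Protocol 8.7 covers patients who discontinue during the double-blind period. Four weeks after the last dose they come in, and "the same safety assessments as the ones planned for study completer's week 52 visit (V31) should be performed". The content of that visit is in 8.5, which begins "A safety follow-up for all patients will be conducted 4 weeks (+/- 7 days) after the final dose of study medication and will include" and then lists physical examination, blood pressure and heart rate, vital signs, ECG, treatments, adverse events, urinalysis, serum biochemistry, and haematology with coagulation. No antibody sample is listed.

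Antibody timing is given in two places. Section 8.8.5: "Specimen will be collected for anti-ApoA-1 antibody testing at the screening visit, week 8, 24 and end of treatment period". Section 8.3: "Anti-ApoA-1 antibody assessment will be performed at week 8, week 24 and week 48 (end of treatment"), which fixes the end of treatment at W48. Section 8.3 also sets the order of sampling and dosing: "Unless otherwise specified, blood and urine specimens will be collected prior to study drug dosing".

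Section 8.7 adds further follow-up. A patient who stops before W24 and agrees to stay is followed on: "he/she will be asked to come back at the site for full assessments as per protocol every 8 weeks until visit V30". For a stop after W24 no such condition is stated: "patient should come back to the site for full assessments as per protocol every 8 weeks until week 48".

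The antibody is a safety assessment in 8.8, and the synopsis includes it among the secondary safety parameters. SAP 7.5.3 lists the haematology, biochemistry and urinalysis parameters to be summarised. Anti-ApoA-1 antibody is not among them.

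**The concern.** Infusion reactions, including hypersensitivity and anaphylaxis, are the one possible exception to a placebo-like safety profile in Protocol 3.3.2, and section 5 says they were more frequent on CER-001. Section 10.2 gives drug-related adverse events and tolerability problems as grounds for stopping. A patient who stops after such a reaction is one whose antibody status matters, yet nothing requires a sample at that point.

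Two things are at stake. First, whether a result is missing may be related to what it would have been, so the incidence among tested patients may not represent the arm. Second, 8.8.5 starts monthly retesting from a positive neutralising result at the end-of-treatment visit. A patient who has left by then has no such sample, so the protocol's own follow-up rule cannot start. A sample not drawn cannot be recovered later.

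**Working it through.** **1. Which exposure is followed by a scheduled sample.** Infusions are weekly from W0 to W8 (9) and every two weeks from W10 to W48 (20), 29 in all. Samples are taken before dosing. The table assumes that the patient attends every sample up to stopping, then the four-week visit, and then leaves.

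| Stops | Post-dose antibody results | Infusions since the last antibody sample |
|---|---|---|
| before W8 | 0 | up to 8 (W0 to W7) |
| W8 to before W24 | 1 (W8) | up to 8 (W8 to W22) |
| W24 to before W48 | 2 (W8, W24) | up to 12 (W24 to W46) |

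Check: 8 + 8 + 12 + 1 (the W48 infusion) = 29. Having no on-treatment result at all is confined to the first row. In the other rows the gap is the exposure after the last sample.

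**2. Whether the later visits in 8.7 close the gap.** Before W24 they depend on the patient agreeing to stay. The full assessments they call for are not itemised. The nearest definition, the complete assessments in 8.3, points to the visit 2 list in 8.2, which has no antibody. If the eight-week interval runs from the stop date, the visits need not fall on W24 or W48. Read together with 8.3 and 8.8.5, they may give off-drug samples at the remaining scheduled times, but the text does not settle this.

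**3. How many patients.** Protocol 12.4 plans 24 completers and allows for 20% discontinuation: 24 / (1 − 0.20) = 30 randomised, which matches the plan. At 2:1 the CER-001 arm has 30 × 2/3 = 20. Expected discontinuations are 30 × 0.20 = 6 overall and 20 × 0.20 = 4 on CER-001. This rate is an all-cause allowance and gives no split by timing or reason.

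**4. What missing results can do to the incidence.** SAP 7.1.2 leaves missing values out of percentages. With u untested patients out of 20 and x positives among those tested, the observed rate is x / (20 − u). The rate in the whole arm lies between x/20 (none of the untested positive) and (x + u)/20 (all positive). The documents give no antibody rate, so x and u are assumptions.

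| u | Observed | Range for all 20 |
|---|---|---|
| 1 | 0/19 = 0% | 0 to 5% |
| 1 | 1/19 = 5.3% | 5 to 10% |
| 2 | 0/18 = 0% | 0 to 10% |
| 4 | 0/16 = 0% | 0 to 20% |
| 4 | 1/16 = 6.3% | 5 to 25% |
| 4 | 2/16 = 12.5% | 10 to 30% |

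Each untested patient widens the range by 1/20 = 5 percentage points. The case u = 4 is extreme: all four expected CER-001 discontinuations would have to occur before W8, and all four patients would have to leave untested. The bias can go either way. With 1/16 observed and no untested patient positive, 6.3% overstates the true 5%.

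**The case against.** The strongest reply is that few patients are affected. Anyone who attends W8 and stops later has at least one on-treatment result. Section 8.7 provides continued visits, and 9.12 says that patients who discontinue should be followed as if they had completed treatment. Section 8.8.4 allows any scheduled blood sample to be analysed for any protocol test. Patients who refuse all visits get only a telephone call under 9.12, so an added tube would not reach them. In the earlier open-label study in this disease (Protocol 3.3.2), no patient stopped for an adverse event.

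Most of this stands, and it narrows the point. It does not remove it. The 8.8.4 provision is permissive, and 8.8.5 supplies antibody tubes only in the kits for its named visits. The continued visits are conditional before W24 and are not itemised for antibody.

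Appendix A needs care. In the copy available to me the last antibody mark falls under V31, which would put the antibody in the early-stop visit. The infusion and MRI rows end in the same column, where they can only mean W48, so the alignment is unreliable. I followed the text; the original table should be checked. Section 8.8.5 could also be read as meaning the patient's own end of treatment. On that reading it would conflict with 8.5 and 8.7, which list no such sample.

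A reader might go further and infer that early stoppers in general have no on-treatment result, or that incidence will be understated because those who react are the ones who test positive. The documents support neither. The first fails for stops from W8 on. The second needs untested patients to be positive more often than tested ones, and no antibody rate or link between antibody and reactions in patients is given.

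**Conclusion.** The gap is real but narrow. As the text is written, no antibody sample is required on early discontinuation, although the antibody is a named safety parameter. The patients affected are those who stop before W8 and leave after the four-week visit (no post-dose result) and those who stop between scheduled samples and leave (none after the later exposure). How many there will be is unknown. About 4 early stops are expected on CER-001 if the 20% allowance applies equally to both arms, and only some of them would fit the description.

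The consequence is a possible bias in antibody incidence of unknown size and direction, bounded at 5 percentage points per untested patient in an arm of 20, together with a follow-up rule that cannot start for these patients. This rests on reading the end of treatment as W48, as 8.3 does, and on V31 carrying no antibody sample, as 8.5 implies. The SAP makes matters worse because it defines no antibody summary, so nothing says how untested patients would be counted. The change is worth making because it is cheap and the information cannot be recovered afterwards.

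**What to change.** 1. In Protocol 8.7, add an anti-ApoA-1 antibody sample, with the neutralising test on positives, to the blood draw at the early-stop safety visit, and supply the tube in that visit's kit.
2. Reconcile 8.3, 8.5, 8.7, 8.8.5 and Appendix A. State whether V31 carries an antibody sample, whether the full assessments in 8.7 include it, from which date the eight-week interval runs, and whether a positive neutralising result at the early-stop visit starts the monthly follow-up.
3. In SAP 7.5.3, add an antibody summary by arm. Count treatment-emergent positivity on any post-dose sample, show patients positive at screening separately, and report the number with no post-dose sample. The wording must admit the early-stop sample, because the visit lists in 7.5.3 end at W48.

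Cost: one extra tube at an existing blood draw in about 6 patients, a short amendment, and updates to the laboratory manual and SAP. It does not reach patients who refuse all visits; reporting the number untested makes that remainder visible.

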#### **8.8 Assessment of Safety**

During double-blind treatment period, all patients who receive at least one dose of study medication and have a subsequent safety evaluation will be included in the safety analyses.

Safety assessments will include:

- Physical exam
- Vital signs assessments
- Electrocardiogram (ECG) assessments

- Laboratory tests
- Adverse events (AEs)
- Metabolic parameters
- Urinalysis
- Anti-ApoA-1 antibody

During open-labeled treatment period, all patients who receive at least one dose of CER-001 and have a subsequent safety evaluation will be included in the safety analyses.

Safety assessments will include Adverse Events (AEs).

### **8.8.1 Physical Exam**

The Investigator or qualified designee will perform a complete physical examination at Screening, Baseline, week 4, week 8 and every 8 weeks until the end of treatment. Additionally, a last physical examination will be done at the end of follow-up visit. Height will be collected at the screening visit only. The complete physical examination should include assessment of general appearance, HEENT/neck, pulmonary system, cardiovascular system, abdomen, extremities, musculoskeletal system, neurological system, and skin. Any findings that differ from the screening visit will be noted and if adverse and clinically significant, in the judgment of the Investigator, will be reported on the adverse event form.

### **8.8.2 Vital Signs**

Temperature in degree centigrade and respiratory rate (RR) should be measured at the screening visit, randomization, at week 4, week 8 and every 8 weeks until the end of treatment. Additionally, assessment of vital signs will be done at the end of follow-up visit. Respiratory rate should be measured by counting the number of respirations for 30 seconds, and then multiplying by 2 in order to obtain the RR per minute. The patient's pulse should be measured for 30 seconds, and then multiplied by 2 in order to obtain HR per minute.

Blood pressure (BP) and heart rate (HR) should be measured at screening visit, randomization, pre-infusion and post-infusion (after the post-infusion observation period prior to the patient leaving the clinic) at week 4, week 8 and every 8 weeks until the end of treatment. Additionally, a last BP assessment will be done at the end of follow-up visit. BP and HR measurements should be determined after the patient has been seated for at least 5 minutes. At the screening visit, the BP will be measured twice in each arm in order to determine the arm to use for subsequent measurement (unless a concomitant condition favors the use of a particular arm), using an appropriately sized cuff. The second BP measure should be taken at least 2 minutes following the first measure. The arm with the higher average systolic reading will then be used for single determinations of BP throughout the remainder of the study. If patient has a systolic blood pressure (SBP) reading of >160mmHg at time of randomization the Investigator, in consultation with the patient may measure again if able to randomize within the allowed window.

### **8.8.3 Electrocardiograms**

Protocol-specified ECGs will be acquired. 12 lead ECGs will be performed using equipment on site at screening visit, randomization, week 4, week 8 and every 8 weeks until the end of treatment. Additionally, a last ECG will be done at the end of follow-up visit. The Investigator will perform standard interpretations of all tracings with results documented in the appropriate source documents and CRFs.

It is the responsibility of the Investigator to obtain additional ECGs required for the clinical management of the patient. All ECGs supporting any suspected MACE or other SAE/AE during the course of the study period, wherever performed, will be reported in the eCRF.

### **8.8.4 Clinical Laboratory Tests**

Laboratory tests should be measured at the screening visit, randomization, at week 4, week 8 and every 8 weeks thereafter until the end of treatment. Additionally, laboratory tests will be done at the follow-up visit. Any blood sample collected according to the Schedule of Assessments (Appendix A) may be analyzed for any of the tests outlined in the protocol. This may also include, but is not limited to, investigation of unexpected results and incurred sample reanalysis.

Clinical laboratory safety testing during the screening and treatment periods will be performed by a central laboratory. Collection kits, shipment instructions, and a detailed clinical laboratory manual will be provided to the study sites. Investigators are required to review the labs upon receipt and make a determination of clinical significance for labs outside of the normal range. All laboratory reports must be reviewed, signed and dated by a medically trained investigator. Clinical laboratory safety testing will consist of the following panels of laboratory tests. The details of which tests are performed at each visit can be found in Appendix A.

## **CHEMISTRY PROFILE**

Glucose

Blood Urea Nitrogen (BUN)

Creatinine

Total Bilirubin

Indirect Bilirubin

Aspartame Aminotransferase (AST/SGOT)

Alanine Aminotransferase (ALT/SGPT)

Alkaline Phosphatase

Total Protein

Albumin

Lactate Dehydrogenase (LDH)

Creatine Kinase (CK)

Sodium

Potassium

Chloride  
Carbon dioxide  
Uric Acid  
Calcium  
Phosphorous

## **HEMATOLOGY**

White Blood Count  
Red Blood Count  
Hemoglobin  
Hematocrit  
Neutrophils  
Lymphocytes  
Monocytes  
Eosinophils  
Basophils  
Platelets

## **URINALYSIS**

Microalbuminuria  
Specific Gravity  
pH  
Glucose  
Total Protein  
Ketones  
Total Bilirubin  
WBC  
RBC  
Casts

The results of all laboratory tests required by the protocol will be documented and will be transferred to the study database via 21 CFR 11 compliant methodology. All clinically important abnormal laboratory tests occurring during the study will be repeated at appropriate intervals until they return either to baseline or to a level deemed acceptable by the Investigator and the Medical Monitor, or until a diagnosis that explains them is made.

The criteria for determining whether an abnormal objective test finding should be reported as an adverse event are described in *section 11.1*.

A serum pregnancy test will be done at screening visit only. Urinary pregnancy test will be used during the course of the study.

### **8.8.5 Immunogenicity Testing**

Specimen will be collected for anti-ApoA-1 antibody testing at the screening visit, week 8, 24 and end of treatment period. If patients have a positive result for the presence of neutralizing anti-ApoA1 antibody at the end of treatment period visit, the patients must return monthly for testing until the antibodies return to screening value. Collection tubes will be supplied by the central laboratory as part of the visit specific kits for these visits. Collection, processing and shipment instructions will be located in the Laboratory Manual provided to the study sites. The clinical sites will send batch shipments of samples to the central laboratory monthly or sooner depending on local site requirements. An aliquot for specimens that test positive for Anti-ApoA-1 antibody testing will be analyzed for neutralizing antibody activity.

### **8.9 Assessment of Lipid Profiles**

Fasting\* samples for the following lipid profile tests will be obtained at screening visit, baseline, week 8, week 24 and week 48:

- Total Cholesterol
- Unesterified Cholesterol
- Esterified Cholesterol
- LDL Cholesterol
- HDL Cholesterol
- Triglycerides
- Phospholipids
- Apolipoprotein A-1, Apolipoprotein B
- Apolipoprotein profile

\*Patient must have fasted (ie not to take any food or liquids other than water) for 8 hours prior to blood sampling.

Assessment of Lipid Profiles will be performed by a central laboratory. Instructions for the collection, storage and shipment of lipid profile samples will be included in the laboratory manual. There will be no data reporting to the Investigator or the Sponsor for lipid profiles prior to database lock with the exception of screening triglyceride values and any triglyceride value greater than 1000 mg/dL.

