**Clinical**

5. Diagnosis of genetically confirmed HDL-c deficiency due to defects in genes coding for e.g. ABCA1 and/or ApoA-1
6. IF the subject is on lipid-lowering therapy or NEEDS to be treated with lipid-lowering therapy then the subject must be on a stable dose at least 6 weeks prior to the baseline procedures.
7. Background symptomatic or asymptomatic cardiovascular disease should be present as such:
  - For symptomatic cardiovascular disease: i) history of cardio or cerebrovascular events, ii) diagnosed coronary artery disease (CAD), iii) diagnosed carotid or peripheral stenosis, iv) previous myocardial revascularisation - percutaneous coronary intervention (PCI), or coronary artery bypass graft (CABG).
  - For asymptomatic cardiovascular disease: patients with subclinical atherosclerosis diagnosed using imaging method such as i)vDoppler ultrasound, ii)vB-mode ultrasonography – measurement of carotid intima media thickness, iii)vintravascular ultrasonography, iv) Computed Tomography, v) Magnetic Resonance Imaging
8. ApoA-1  $\leq$  110 mg/dL
9. HDL-cholesterol  $\leq$  35 mg/dL or 0.9 mmol/L

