**7.3 Exclusion criteria**

**Patients meeting any one of the following criteria are not eligible for the study:**

**Medical Status**

1. Patient with LCAT mutation will be excluded
2. Patient who experienced a cardiovascular event within 6 months prior to the onset of screening
3. Patient who experienced stroke or other cerebrovascular event within 1 year prior to the onset of screening
4. Patient with triglycerides level above 500 mg/dL
5. The patient has evidence of clinically significant, uncontrolled or unstable cardiovascular, renal, hepatic (incl. AST or ALT at or above 3x ULN, or bilirubin at or above 2x ULN), gastrointestinal, hematologic, immunological, neurological, endocrine, metabolic or pulmonary disease (as determined by medical history, clinical laboratory or ECG results, or physical examination) or any other medical disorder that would increase the risk associated with taking study medication or would confound the interpretation of study results
6. Patients with a body mass index (BMI)  $<$  17 kg/m^2 or  $>$  40 kg/m^2
7. Patients with severe anemia defined as hemoglobin level below or equal to 10 g/dL
8. Any clinically significant abnormal laboratory data, vital signs, physical examination at screening or baseline, which in the opinion of the investigator, would interfere with safety assessments

9. Clinically significant electrocardiogram (ECG) abnormality at screening, including sinus bradycardia (resting heart rate < 50 beats per minute), 2nd or 3rd degree atrioventricular block, prolonged QTc (QTcF  $\geq$  450 ms in males and  $\geq$  470 ms in females) history of congenital long QT syndromes, or risk of Torsades de Pointes because of family history of sudden death, etc.
10. Positive result on the serum pregnancy test or are breast feeding at screening, or intend to become pregnant during the course of the trial
11. Male intending to father a child during the study
12. Likely to be unreliable as a study participant based on the Investigator's (or designee's) knowledge of the patient (e.g., alcohol or other drug abuse, inability or unwillingness to adhere to the protocol, or psychosis)
13. Symptomatic (NYHA Class II or greater) congestive heart failure requiring and persisting despite appropriate medical treatment
14. Uncontrolled blood pressure: systolic blood pressure  $\geq$ 160 mmHg and/or diastolic blood pressure  $\geq$ 100 mmHg at screening or any other pre-randomization visit

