## 8.1 Screening Examination and Eligibility Screening Form

All patients must provide written informed consent before any study specific assessments or procedures are performed. An Eligibility Screening Form (ESF) documenting the investigator's assessment of each screened patient with regard to the protocol's inclusion and exclusion criteria is to be completed by the investigator. A screen failure log must be maintained by the investigator.

### Visit 1

This is the first visit of the study. This visit will be performed after obtaining written informed consent. The investigator will advise the patient on heart healthy diet and life style.

Screening assessments include:

- Informed Consent
- Inclusion/exclusion criteria
- Demographic information
- Smoking status
- Measurement of height and body weight
- Medical history/surgical history and concomitant diseases
- Previous and concomitant treatments
- Physical exam (See Section 8.8.1)
- Vital Signs (See Section 8.8.2)
- Blood Pressure and Heart Rate
- ECG (See Section 8.8.3)
- Serum biochemistry (See Section 8.8.4)
- Hematology and coagulation (See Section 8.8.4)
- Urinalysis (See Section 8.8.4)
- Fasting lipid profile (See Section 8.9), including Apolipoprotein profile.
- Anti-ApoA-1 antibody (See Section 8.8.5)
- Markers of inflammation, oxidation, lipid metabolism and CV risk (See Section 8.10)
- Serum pregnancy test in female patients (See Section 11.8)
- FSH (only for women whose last menstrual period was between 6 and 12 months before screening)
- Fasting blood glucose and HbA1c
- Creatinine and/or BUN testing to determine GFR

Patient must have fasted (ie not to take any food or liquids other than water) for 8 hours prior to blood sampling.

A DNA sample will be taken ONLY for determination of the presence of HDL gene mutations specifically for ABCA1 and/or ApoA-1 mutation(s) to ensure that the patient was to satisfy all inclusion and exclusion. Genotyping will be performed at the Robarts Research Institute, London, Canada.

**Following visit 1, if a patient is eligible according to all of the inclusion and exclusion criteria, he/she will be instructed to come in fasted for the randomization visit 2.**

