## **9.11 Maintaining the Blind**

Study drug will be dispensed by an unblinded Study Pharmacist or designee who will be unblinded as described in Section above (Section 9.10). The study patients, Investigator, sponsor and study site personnel and site monitors will remain blinded to the treatment. During the study, and prior to database lock, no lipid profile data will be reported to the Investigator or to the Sponsor. Data will be reviewed in a blinded manner.

Randomization list is kept strictly confidential, accessible only to authorized persons, until the time of unblinding. It is the responsibility of the Pharmacist to maintain the blind throughout the study.

The randomization code may be broken if an emergency situation arises that in the Investigator's opinion requires the knowledge of the code (for example, life threatening situation or necessity to know the product administered to provide with the best medical care). The investigator must do his/her very best to contact the Sponsor before unblinding the code using an Interactive Web Response System (IWRS). Date, time, and reason(s) for breaking the code must be recorded by the Investigator in IWRS.

At the conclusion of the trial, the occurrence of any emergency code breaks will be verified after return of all code break reports and unused drug supplies to the packaging supplier.

The CRO mandated for pharmacovigilance reserves the right to break the blind for SAEs which are considered as related to the study drug and unexpected, which could require an expedited report to the regulatory authorities.

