6.1 Analysis populations of patients

The statistical analysis will be based on the three populations defined below. To be part of a population, patients should have signed informed consent and fullfill all inclusion / exclusion criteria. Some criteria have been added after the start of the study. Hence patients included before will be considered as compliant to these criteria via a Not Applicable (NA) status.

Safety population

The safety population will comprise all randomized patients who received at least one dose of study medication.

Safety analysis will be performed on the safety population according to the actual treatment received.

Modified Intent-To-Treat (mITT) population

The mITT population will comprise all randomized patients for whom at least one of the following conditions is satisfied:

- 3T-MRI assessment available at baseline (W0) and at least one post-baseline 3T-MRI assessment available
- 18FDG-PET/CT assessment available at baseline (W0) and at least one post-baseline 18FDG-PET/CT assessment available

Per Protocol (PP) population

The PP population will comprise all patients of the mITT population without any major protocol deviations (*Cf.* section 6.3).

Defining study populations and excluding patients from the analysis will be a joint decision taken by Sponsor and ICTA PM' representatives (Statistician and Project Leader). Patients to be excluded and

CER-001-CLIN-009 CER-001

reasons for their exclusion will be discussed during data review meetings, before database lock and unblinding.

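### Screening HDL-C and ApoA-1 decide eligibility, yet Protocol 8.9 withholds them from the investigator and sponsor until database lock, and 8.9 and 9.11 disagree on what is withheld

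*Protocol*

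**What the plan says.** Protocol 7.2 sets an upper limit of 110 mg/dL for ApoA-1 (criterion 8) and of "35 mg/dL or 0.9 mmol/L" for HDL-C (criterion 9). Sections 8.1, 8.2 and 9.9 require every criterion to be met before the patient is randomised at visit 2, and section 8.1 has the investigator record the assessment on an Eligibility Screening Form.

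The visit 1 list in section 8.1 includes "Fasting lipid profile (See Section 8.9), including Apolipoprotein profile". Section 8.9 names HDL cholesterol and apolipoprotein A-1 as components of that profile and assigns it to a central laboratory. It then stops lipid results from reaching the investigator or the sponsor before database lock, "with the exception of screening triglyceride values and any triglyceride value greater than 1000 mg/dL".

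Section 9.11 restates the restriction for the period before lock: "no lipid profile data will be reported to the Investigator or to the Sponsor". It lists no exception.

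SAP 6.1 says that to belong to any analysis population, "patients should have signed informed consent and fullfill all inclusion / exclusion criteria". The sponsor and the CRO decide exclusions jointly at data review meetings held before lock and unblinding. SAP 6.2 finalises the deviation list, which covers the entry criteria, at the same stage.

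**The concern.** Withholding lipid results protects the blind, because an infused ApoA-1 product can be expected to shift on-treatment lipids. That reason does not apply to a sample taken before randomisation. Here the restriction reaches back to screening and covers two quantities that the entry criteria depend on.

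The triglyceride exception suggests an oversight. Exclusion criterion 4 reads "Patient with triglycerides level above 500 mg/dL", and 8.9 releases the screening triglyceride value that this criterion needs. It does nothing equivalent for the other two lipid limits.

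Two things are at stake. At randomisation, the investigator is asked to certify criteria 8 and 9 without the protocol's own result. At the data review, one of the two parties deciding the populations does not have the values that SAP 6.1 makes a condition of membership.

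**Working it through.** The point rests on comparing sections, so the comparison comes first and the arithmetic only gives scale.

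**Comparison of the sections**

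| Lipid entry criterion | Scheduled screening test | Released before lock under 8.9? | Released under 9.11? |
|---|---|---|---|
| Triglycerides above 500 mg/dL (exclusion 4) | Central profile, visit 1 | Yes | No |
| ApoA-1 at or below 110 mg/dL (inclusion 8) | Central profile, visit 1 | No | No |
| HDL-C at or below 35 mg/dL (inclusion 9) | Central profile, visit 1 | No | No |

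1. The 8.9 restriction does cover screening samples. An exception for screening triglycerides would be needless otherwise.
2. The visit 2 profile does not help. It is taken at the randomisation visit, goes to the same central laboratory and falls under the same restriction.
3. No section says that a local or historical HDL-C or ApoA-1 value may be used, or which value decides.
4. The first row shows the separate conflict: 8.9 releases screening triglycerides, and any triglyceride above 1000 mg/dL, while 9.11 releases nothing.
5. SAP 6.1 places the population decision before lock, which is the period in which 8.9 and 9.11 keep these values from the sponsor.

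**Scale (assumed illustration; the documents give no rate of ineligibility)**

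- Inputs: 30 randomised, 2:1 (Protocol 6.4 and 12.4).
- Expected placebo arm: 30 × 1/3 = 10.
- One ineligible patient: 1/30 = 3.3% of the sample, or 1/10 = 10% of placebo if allocated there.

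**The plan's power figure, for context**

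Protocol 12.4 states 90% power with 16 + 8 completers, a difference of 6.7% and an SD of 4.5%, at two-sided 0.05. With the two-sample t-test:

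- Noncentrality = 6.7 / (4.5 × √(1/16 + 1/8)) = 6.7 / (4.5 × 0.433) = 3.44, on 22 degrees of freedom.
- Power = 90.7%, which reproduces the stated 90%.
- Completers allowing for dropout: 24 / 0.8 = 30, which matches the planned total.

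If ineligible patients were removed from those 24 completers, the same formula gives:

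| Assumed removed | Remaining | Power |
|---|---|---|
| 1 (CER-001) | 15 + 8 | 90.0% |
| 3 (2 CER-001, 1 placebo) | 14 + 7 | 86.2% |
| 6 (4 CER-001, 2 placebo) | 12 + 6 | 79.8% |

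These rows show what removals would cost. They do not estimate how many there would be.

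**The case against.** The strongest reply is that the protocol clearly expects the criteria to be assessable. The investigator completes an eligibility form. Footnote 10 of Appendix A ties DNA sampling to patients who meet all the other selection criteria, which implies that lipid status is known by then. Criteria 8 and 9 do not say that the central visit 1 result decides, so a site could rely on a local or earlier value. This stands as far as it goes: nothing forbids such a value. But nothing provides for one either, so the basis for eligibility could differ between sites without anyone breaching the protocol.

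A second reply concerns the data review. The restriction names the investigator and the sponsor, not the CRO. Protocol 8.8.4 sends the results of all protocol-required laboratory tests to the study database, Protocol 12.1 has the CRO check the data, and the CRO shares the population decision. This also stands. A reader might infer that a breach would surface only after lock, and the documents do not support that, because the CRO could find it earlier. What remains is that the sponsor takes part in a joint decision without the values.

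Third, genetic confirmation (criterion 5) does not depend on lipid reporting, which limits the risk of enrolling patients without the disease. That is fair, but criteria 8 and 9 are separate requirements.

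Finally, the CRF and the deviation list attached to the SAP are not available here. They may record how each criterion was checked.

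**Conclusion.** The contradiction is real and should be corrected. The protocol makes two lipid limits a condition of randomisation, schedules one screening test for them, and withholds that test's results from the person who must apply the limits. Sections 8.9 and 9.11 also contradict each other on triglycerides.

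Its extent is limited. The supported statement is that the investigator cannot verify criteria 8 and 9 from the protocol's own screening test, and that the sponsor lacks the values when the populations are settled. A reader might go further and conclude that nobody can check eligibility by any route, or that all 30 patients are affected. The documents support neither conclusion: other measurements are not excluded, the CRO may hold the results, and SAP 6.1 treats patients enrolled before a criterion was added as compliant with it, without saying which criteria were added. Nor do the documents show that any ineligible patient was enrolled.

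The number affected is therefore unknown. The 3% and 10% figures and the power table rest on assumed counts. The power table also assumes that ineligible patients would be dropped in addition to the planned 20% discontinuation.

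**What to change.** 1. **Protocol 8.9:** extend the exception to screening (pre-randomisation) HDL-C and ApoA-1.
2. **Protocol 9.11:** add the same exceptions, including the two triglyceride exceptions that it now omits, so that the sections agree.
3. **Protocol 7.2 and the synopsis:** state which measurement decides criteria 8 and 9. If a local or earlier value is acceptable, say so and define which one.
4. Keep post-dose lipid results withheld as now, apart from the existing exception for triglycerides above 1000 mg/dL.

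With these changes the investigator has the values at randomisation, and the sponsor and the CRO work from the same values at the data review. Screening samples precede allocation and dosing, so releasing them cannot unblind anyone. The cost is a sentence in each affected section and a change to the central laboratory's reporting settings. No new sample or visit is needed.
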